## **2. LIST OF ABBREVIATIONS**

BI	Boehringer Ingelheim
CI	Confidence Interval
CPRD	Clinical Practice Research Databases
CPT	Current Procedural Terminology codes
CTS-PS	Calendar-time specific (CTS) propensity scores (PS)
DPP-4i	Dipeptidyl peptidase 4 inhibitors
EMA	European Medicines Agency
ENCePP	European Network of Centres for Pharmacoepidemiology and Pharmacovigilance
HbA1c	Hemoglobin A1c
HIPAA	Health Insurance Portability and Accountability Act of 1996
HR	Hazard Ratio
HCRU	Healthcare resource utilization
GLP-1 RA	Glucagon-like peptide-1 receptor agonist
ICD-9-CM	International Classification of Diseases, Ninth Revision, Clinical Modification
ICD-10-CM	International Classification of Diseases, Tenth Revision, Clinical Modification
ISPE	International Society for Pharmacoepidemiology
LOINC	Logical Observation Identifiers Names and Codes
NIS	Non interventional study
NPV	Negative Predictive Value
NSAIDs	Non-steroidal anti-inflammatory drugs
Optum CDM	Optum Clininformatics® Data Mart
PASS	Post-authorization safety study
PPV	Positive Predictive Value
PS	Propensity scores
PSUR	Periodic Safety Update Report
PY	Person-Year
RMP	Risk Management Plan
SEAP	Statistical Epidemiological Analysis Plan

SGLT2i	Sodium glucose co-transporter-2 inhibitor
SU	Sulfonylurea
T2DM	Type 2 diabetes mellitus
Truven Marketscan CCAE	Truven Marketscan Commercial Claims and Encounters
Truven Marketscan MDCR	Truven Marketscan Medicare Supplemental (MDCR)
TZD	Thiazolidinediones
UK	United Kingdom
US	United States

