### 9.7.2 Propensity score approach

Decisions to begin a specific hypoglycaemic agent are influenced by demographic, medical, and clinical factors, and same factors might be associated with the outcomes of interest. The propensity score is the predicted probability of being assigned to a particular treatment conditional on a set of observed covariates. Because the models predict the probability of being treated with the exposure drug and not the probability of experiencing the outcome, a high number of variables can be used in the predicting regression model [[P12-04844](#), [R14-5241](#), [R14-5284](#), [R14-5389](#)].

Propensity scores for the comparison of empagliflozin vs. study comparator will be generated. Furthermore, given the different inclusion/exclusion criteria used for each treatment line cohort, the propensity scores will be cohort specific (i.e., propensity scores will be calculated for the monotherapy, dual therapy and triple therapy cohorts separately).

As a first step, a propensity score is estimated for each cohort member at the index date, based on the values of the observed covariates during the look-back period. In this study, propensity scores will be estimated by conducting multivariable logistic regression modelling and incorporating measured potential predictors of therapy as independent variables and exposure group status (empagliflozin group vs. comparator) as the outcome.

We will use PS matching to balance a number of covariates. Key advantages of PS matching are that large numbers of covariates can be adjusted even when studying infrequent outcomes, the achieved covariate balance can be documented, multiple outcomes can be studied after a single matching process, [R13-1120] and patients who cannot find comparable pairs will be implicitly dropped out of the analysis increasing the validity of findings [R17-1404].

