The propensity score will be used to match patients in a 1:1 ratio using a nearest-neighbor algorithm and calipers of width equal to 0.2 of the standard deviation of the logit of the estimated propensity score [R13-3590, R18-2599, R16-1227]. A 1:n variable ratio matching will not be used as it involves several complications while providing only a minimal gain in estimation precision [R17-1267]. If balance is not achieved, the PS model will be refitted using interaction terms [R18-2599]. PS balance achievement will be inspected by tabulating all patient characteristics by treatment status and by assessing the standardized differences. Any patient characteristics with a standardized difference of >10% will be considered for additional post-matching adjustment [R13-3590].

With the publication of EMPA-REG OUTCOME trial results in September 2015 and the approval of a separate indication to reduce the risk of cardiovascular death in adults with T2DM and established cardiovascular disease by the US FDA in December 2016, the characteristics of patients initiating empagliflozin has likely changed during the study period. To account for patient characteristics changing over time, patients will be matched on the calendar quarter-year of initiation of the study medication. If we lose too many patients using this method, we may instead decide to match on year of initiation of index medication and then include calendar quarter-year variable in the PS model.

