ANNEX 3. STUDY COVARIATES

N	Category	Variables	Definition
1	Demographics	Age	
 - By year - By category (18-54, 55-64, 65-74, 75+)
		Gender	
 - Male, Female
		Smoking	
All codes could be found in the following excel file:
  
1245-0201%20codes%20part%201_03022

		Alcohol abuse or dependence	
		Drug abuse or dependence	
		Overweight	
		Obesity	
		Calendar quarter of cohort entry	
2	Comorbidity indexes	Elixhauser comorbidity index	
 - R14-4775
		Charlson comorbidity index	
3	Diabetes specific complications	Diabetes retinal problems	
Diabetic retinopathy, diabetes with other ophthalmic manifestations, Retinal detachment, vitreous hemorrhage, vitrectomy, retinal laser coagulation therapy. Codes presented in the following excel file:
  
1245-0201%20codes%20part%201_03022

		Diabetic neuropathy	
		Diabetic nephropathy	
		Hypoglycaemia	
		Hyperglycaemia	
		Disorders of fluid electrolyte and acid-base balance	
		Diabetic ketoacidosis	
		Hyperosmolar hyperglycemic nonketotic syndrome (HONK)	
		Diabetes with peripheral circulatory disorders	
		Diabetic foot	
		Gangrene	
		Lower extremity amputation (lower extremity amputation diagnosis code, lower extremity amputation procedure code (ICD), lower extremity amputation procedure code (CPT).)	
		Osteomyelitis	
		Skin infections	
		Erectile dysfunction	
		Diabetes with unspecified complication	
		Diabetes mellitus without mention of complications	

BOEHRINGER INGELHEIM Group of Companies
Statistical and Epidemiological Analysis Plan (SEAP) for Non-Interventional Studies (NIS)

c37922104-02

Page 23 of 27

Proprietary confidential information © 2022 Boehringer Ingelheim International GmbH or one or more of its affiliated companies

4	General medical history	Hypertension	Codes presented in the following excel file:  1245-0201%20codes%20part%202_03022
		Hyperlipidaemia	
		Myocardial infarction (Acute MI and old MI)	
		Angina (ACS/unstable angina, stable angina)	
		Coronary atherosclerosis and other forms of chronic ischemic heart disease	
		Cardiac procedures (Previous cardiac procedure (CABG or PTCA or Stent))	
		Ischemic stroke (w and w/o mention of cerebral infarction)	
		Hemorrhagic stroke	
		TIA	
		Cerebrovascular disease (Other cerebrovascular disease, late effects of cerebrovascular disease, Cerebrovascular procedure)	
		Heart failure (CHF)	
		Peripheral Vascular disease or PVD surgery	

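### The visible propensity model cannot follow the prescribing change the protocol expects; the pooled hazard ratio is little affected, but balance within period and the eCVD subgroups are exposed.

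*Protocol*

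**What the plan says.** Protocol 9.7.2 states that "the characteristics of patients initiating empagliflozin has likely changed during the study period". It gives two dated causes: the publication of a cardiovascular outcome trial in September 2015, and the US "approval of a separate indication to reduce the risk of cardiovascular death in adults with T2DM and established cardiovascular disease" in December 2016.

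On the model, it says that "propensity scores will be estimated by conducting multivariable logistic regression modelling and incorporating measured potential predictors of therapy as independent variables", and that "propensity scores will be calculated for the monotherapy, dual therapy and triple therapy cohorts separately". No visible step makes the score specific to calendar period.

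On calendar time, the rule is: "To account for patient characteristics changing over time, patients will be matched on the calendar quarter-year of initiation of the study medication". If too many patients are lost, the fallback is to "match on year of initiation of index medication and then include calendar quarter-year variable in the PS model". SAP 10.2 only refers back to the protocol. SAP Annex 3 lists "Calendar quarter of cohort entry" among the demographic covariates, with no interaction.

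On balance, 9.7.2 tabulates characteristics by treatment group and looks at standardized differences. A value above 10% leads to considering further adjustment. Interaction terms enter only in a refit after balance has failed, and calendar time is not named among them. No table by calendar period is planned.

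Two other places matter. Protocol 9.7.6, item 4, plans subgroup analyses by eCVD history and does not mention re-matching. Protocol 9.9.2 describes quarter matching as a step that follows PS matching, which does not fit 9.7.2.

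**The concern.** A cardiovascular indication changes how strongly cardiovascular disease predicts the choice of empagliflozin. A model with one coefficient per covariate estimates an average of the early and late relations. It is then wrong in opposite directions before and after the change. Two patients with the same score in the same quarter did start at the same time, but their cardiovascular profiles need not be comparable.

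The fallback has the same gap, because a main effect for quarter moves the intercept and leaves the covariate coefficients alone.

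The planned check pools all periods, so early and late errors can offset each other. The table then passes and the interaction refit is never triggered. This matters because Protocol section 7 names eCVD as a risk factor for acute pancreatitis, and because a planned subgroup analysis splits on it.

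**Working it through.** **1. The plan's own figure.** Protocol 9.5 gives 34585.4 per group for rates of 0.0022 in both groups, ratio margin 1.5, one-sided alpha 0.05 and power 80%. The Farrington-Manning formula is n = [z_a sqrt(V0) + z_b sqrt(V1)]^2 / (p2 - 1.5 p1)^2. The restricted estimates are 0.0017598 and 0.0026398.
- V0 = 0.0026398 x 0.99736 + 2.25 x 0.0017598 x 0.99824 = 0.0065855
- V1 = 3.25 x 0.0022 x 0.9978 = 0.0071343
- n = (1.6449 x 0.08115 + 0.8416 x 0.08446)^2 / 0.0011^2, about 34585

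The figure reproduces, and nothing below changes it.

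**2. Why the errors offset.** Let A be treatment, e the fitted score and X the eCVD indicator. A logistic model with quarter terms forces the sum of (A - e) to zero in each quarter. It forces the sum of (A - e)X to zero only over the whole cohort. Any early error in X is therefore paid back late. Covariate-by-period terms force that second sum to zero within each period.

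**3. Size of the imbalance.** The documents give no odds ratios, eCVD prevalence or uptake, so these are assumptions. The simulation used 150,000 patients, 27 quarters, 20% eCVD and 10 other covariates. Matching was 1:1 nearest neighbour within quarter with a caliper of 0.2 SD of the logit, and each scenario was run three times. The standardized difference is d = (pT - pC) / sqrt{[pT(1 - pT) + pC(1 - pC)] / 2}. The bias factor is the ratio of expected risk in the empagliflozin arm to that in the comparator arm, here with eCVD doubling the risk (assumed).

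| eCVD odds ratio before / from 2017 | Pairs before 2017 | d overall | d before | d from 2017 | Pooled bias, equal follow-up | Pooled bias, early follow-up x3 |
|---|---|---|---|---|---|---|
| 0.67 / 1.5 | 15% | 1.2% | -23.9% | +5.2% | 1.004 | 0.986 |
| 1.0 / 1.5 | 15% | 0.4% | -12.4% | +2.5% | 1.001 | 0.992 |
| 1.0 / 2.0 | 15% | 1.0% | -22.5% | +5.0% | 1.003 | 0.986 |
| 0.67 / 1.5 | 35% | 0.2% | -19.9% | +10.4% | 1.001 | 0.975 |
| 1.3 / 1.3 (no change) | 15% | -0.6% | +0.6% | -0.8% | 0.998 | 0.999 |

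A hand check of the first row: 0.15 x (-23.9) + 0.85 x 5.2 = +0.8%, close to the simulated 1.2%. Leaving quarter out of the PS gives the same pattern. In all four change scenarios the overall check passes and the early period fails.

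**4. Size against the margin.** The largest pooled shift is 0.975. ln(0.975) = -0.025 and ln(1.5) = 0.405, so it is about 6% of the distance to the margin. A stronger assumed reversal (log-odds -0.5 to +0.7, eCVD risk ratio up to 2.5) still gave pooled factors of only 0.97 to 1.01.

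**5. The eCVD subgroup.** Quarter matching equalises start dates over all pairs, not among eCVD patients alone. If empagliflozin users have less eCVD than their matches early and more late, then within the eCVD stratum they started later. In one simulated shift, 9% of empagliflozin users and 15% of comparators in that stratum started before 2017. Then d = 0.06 / sqrt[(0.09 x 0.91 + 0.15 x 0.85) / 2] = 0.06 / 0.324 = 0.185 (rounded inputs). Over the range of assumed shifts it ran from about 9% to about 18%, most of it above the plan's own 10% limit.

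**6. With covariate-by-period terms.** In the first scenario the differences become -0.3% overall, -1.4% before and -0.1% from 2017, with 28,042 pairs against 28,043. In the fourth, pairs fall from 35,132 to 35,056 (0.2%). The period difference inside the eCVD stratum drops to about 2% or less in nearly all runs.

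**The case against.** The strongest reply is that the one powered analysis hardly moves. The main result is a pooled dual-therapy hazard ratio, no period-specific ratio is planned, and imbalances that cancel overall mostly cancel in the estimate as well. This stands. A reader might infer that the non-inferiority conclusion is at risk, and the figures do not support that.

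A reader might also suppose that early entrants have the longest follow-up, so that the cancellation fails in person-time. The documents do not say so. Main-analysis follow-up ends at discontinuation plus 30 days, or at a censoring switch or addition, and so depends largely on persistence. The intention-to-treat sensitivity analysis fixes follow-up at 12 months. The threefold ratio used above is a stress case.

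The protocol's abbreviation list contains "Calendar-time specific (CTS) propensity scores (PS", which the visible methods never use. It is tempting to read this as a dropped method. However, the section numbers skip 9.7.5 in the protocol and 10.5 in the SAP, and two SAP pages show only running headers, so the term may belong to text that is not visible. It is not evidence against the plan. Likewise, nowhere does the plan write that one model covers the whole period. That follows from the score being made specific to treatment line only, and it may mean one model per database.

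Quarter matching is also a legitimate control, since it stops early starters being compared with late ones. Subgrouping by eCVD largely removes confounding by recorded eCVD itself. That is true, but the same split breaks the quarter match. Finally, the planned model uses many separate cardiovascular items (SAP Annex 3), so a single eCVD indicator only illustrates the mechanism.

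**Conclusion.** The point holds in a limited form. On the visible text, the step offered against changing prescribing aligns start dates but leaves covariate coefficients fixed over time, and the balance check that would trigger interaction terms is not split by period. Under the assumed shifts, eCVD can be out of balance by 12% to 24% before 2017, with the opposite sign afterwards, while the overall figure stays near 1%.

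The expected effect on the pooled dual-therapy hazard ratio is about 1%, and up to about 2.5% if early pairs have three times the follow-up. Neither threatens the 1.5 margin. The main harm is to balance within period and to the eCVD subgroup comparison, where calendar period can differ by about 9% to 18% if patients are not re-matched.

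All of these sizes rest on assumed odds ratios, prevalence, uptake and eCVD risk ratios. The protocol says only that a change is likely, not how large it is or that any association reversed. If nothing changed, the imbalance disappears.

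**What to change.** In Protocol 9.7.2:
- Include covariate-by-calendar-period terms in the PS from the start, at least before and after December 2016 for the cardiovascular covariates, or estimate the PS separately by period.
- Keep the quarter match.
- Tabulate standardized differences by period and within the eCVD strata as well as overall, including calendar period itself within those strata. Refit if any exceeds 10%.
- Apply the same terms if the year-matching fallback is used.

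Reconcile 9.7.2 with 9.9.2 on whether quarter matching is done together with PS matching or after it.

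The cost is a few lines of code and one more balance table. Almost no pairs are lost. The drawback is slightly less stable PS estimates in the sparse launch quarters.

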### **9.7.3 Main analysis**

The study will be conducted utilizing a modified “as-treated” approach. Users of empagliflozin or a comparator oral non-incretin/non-SGLT2i-containing hypoglycaemic agent will be considered exposed from the date of first prescription claim until earliest claim for acute pancreatitis or until one of the following censoring criteria have been met (Table 3):

- The date of end of continuous registration in the database
- The date of death
- The date of study end
- The date of discontinuation of index medication (defined as the date of the last date of last dispensing + days supply + grace period). The grace period is a time period after exposure end during which observed outcomes are still attributed to the exposure. Grace

period varies according to the specific outcome. In this study, for acute pancreatitis, we have 30 days grace period in the main analysis [[c18659315-02](#)] and 90 days in the sensitivity analysis [[R18-1760](#), [RRA-21430](#), [P20-07536](#)].

- The date of switch of index medication to another hypoglycaemic agent
- The date of addition of incretin-based therapy (with continuation of index therapy)
- The date of addition of SGLT2i (with continuation of index therapy)
- The date of addition of insulin (with continuation of index therapy)
- The date of addition of the within treatment line comparator index drug (with continuation of index therapy)

For those who switch to an incretin therapy/SGLT2i, or switch to the within treatment line comparator, exposure duration will include the last date of known prescription coverage before the switch. For discontinuation of the index drug (with no prescription claim for a new hypoglycemic drug), exposure duration will include the last date of known prescription coverage (date of last prescription fill plus days' supply minus one day) and a grace period equal to 30 days. The last date of known coverage may also be extended further to account for overlap periods – when a prescription is refilled before the previous supply was considered exhausted. Gaps between coverage and prescription refills that are less than the duration of each patient's respective grace period will be considered continuous exposure time. For patients who switch, exposure time will not extend past the date of the first prescription claim for the newly prescribed switch agent.

For patients who add an incretin-based therapy, SGLT2i, or a within treatment line comparator index drug, their data will be censored on the date of the prescription claim for the added medication.

Patients with chronic use of insulin at baseline (see SEAP for definition) in the outpatient setting during the follow-up period will be censored from the study.

From a feasibility assessment conducted in November 2021, it is known that there are not enough study participants in the Optum and MarketScan database in each therapy line and the dual-therapy cohort was reported with the highest number of empagliflozin initiators. Therefore, a meta-analysis of the dual therapy cohorts including the data from the Marketscan MarketScan and Optum databases will be the main analysis of this study

Meta-analysis of different treatment line cohorts with the different comparators (first, second and third line) will not be conducted in this study as patients in these 3 cohorts will likely have very different profiles including different disease stages, and results would be difficult to interpret.

The incidence rates (per 1000 PY) and corresponding 95% confidence intervals (CI) of acute pancreatitis during the follow-up time will be calculated in each exposure group of interest in the unmatched and PS-matched cohorts.

All results will be presented for each database separately but if there is not enough sample size in each treatment line cohort in each database, after evaluating potential heterogeneity, meta-analysis techniques will be used to pool the 2 treatment line cohorts of the 2 databases. Descriptive tables and all parameter estimates from the main and all sensitivity analyses will be pooled using meta-analytic methods assuming a fixed effects model, to avoid potential biases associated with random effects pooling in the context of few databases [R17-1410].

Cox proportional hazards regression models based on time-to first acute pancreatitis event will be used to estimate hazard ratios (HR) and 95% CIs for each treatment line comparison of interest (in each database or in case of limited sample size a meta-analysis of 2 databases) in the unmatched and PS-matched cohorts. Proportionality hazard assumption will be checked using the log rank test.

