## **9.5 STUDY SIZE**

All patients with T2DM who newly initiate therapy with empagliflozin or study comparator who meet the inclusion and exclusion criteria will be included in the analysis.

Event rate of acute pancreatitis reported in patients with T2DM who are treated with canagliflozin was reported to be 2.2 per 1000 PY [\[RRA-21430\]](#). This rate was used for sample size calculation using the formula of Farrington and Manning (maximum likelihood method) [\[R14-3295\]](#).

Null hypothesis H0:  $\pi_2 / \pi_1 \geq 1.5$  (non-inferiority)

A single stage (fixed sample size) design was chosen.

For specified  $\alpha = 0.05$  and rates  $\pi_1 = 0.0022$  and  $\pi_2 = 0.0022$  (odds ratio of 1.000) the power (1 -  $\beta$ ) is 80.0% if the test stages consist of the sample sizes given in the last two columns of [Table 1](#).

The computation assumes an allocation ratio (n2/n1) = 1 (Table 1). It is assumed that all patients have 1 year of follow up.

**Table 1** Number of empagliflozin initiators and empagliflozin-exposed person-years needed to detect a HR of 1.5 and 2.0 with a power of 80% and  $\alpha = 0.05$  under 1:1 matching ratio

Hazard ratio (HR)	Information rate	Bunds accept $H_0$	Bunds reject $H_0$	sign.level one-sided	$\alpha$ spent	$\beta$ spent	power achieved	Observations per exposure group	Overall observations
1.5	1.0	1.645	1.645	0.0500	0.0500	-	0.8000	34585.4	69170.8

ADDPLAN Adaptive Design Software 2019 and SAS 9.4 software ( ) were used to calculate the sample size.

Analysis of this study will be initiated as soon as a sufficient sample size to exclude a HR of 1.5 with 80% power is reached. Based on a feasibility assessment conducted in Optum and MarketScan databases using data between 1 August 2014 and the latest data-cut available in MarketScan (30 September 2020) and Optum (31 March 2021), the dual-therapy cohort was reported with the highest number of empagliflozin initiators, therefore meta-analysis of the dual therapy cohorts including the data from the MarketScan and Optum databases will be the main analysis of this study as it will be the only powered analysis.

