### **9.7.1 Definitions**

- Index date: Date of the first recorded claim for a qualifying prescription of an index medication as a new user.

- Follow-up: Starts from the day after the index date until the first qualifying event has been met (see [Table 2](#) and [3](#)).
- Look-back period: Patients are required to have at least 6 months of continuous registration in the database prior to initiation of an index medication. The look-back period is defined as 6 months prior to the index date and including the index date. The look-back period was specified to confirm new medication use (i.e. having a first prescription claim for empagliflozin or other oral non- incretin/non-SGLT2i-containing hypoglycaemic without use of these medications in the prior 6 months) and describe baseline parameters, such as prior medical history and medications.
- Grace period: 30 days in main analysis [[c18659315-02](#)] and 90 days [[R18-1760](#), [RRA-21430](#), [P20-07536](#)] in sensitivity analysis.

Table 2 Definitions for study end date

Reason for End of Study or censoring (earliest date of options below)	Definition for End Date
Acute pancreatitis event	Date of the first acute pancreatitis using ICD9 or ICD10 codes
Switch of index medication to another hypoglycaemic agent; see Table 3	Last date of known prescription coverage (date of last prescription fill plus days' supply minus one day) and a grace period equal to 30 days. Exposure time will not extend past the date of the first prescription claim for the newly prescribed agent*
Addition of incretin-based therapy (with continuation of index therapy)	Date of the prescription claim for the added incretin therapy
Addition of SGLT2i (with continuation of index therapy)	Date of the prescription claim for the added SGLT2i therapy
Addition of insulin (with continuation of index therapy)	Date of the prescription claim for the added insulin therapy
Addition of the within treatment line comparator index drug; see Table 3 (with continuation of index therapy)	Date of the prescription claim for the added treatment line comparator index drug
Discontinuation of index drug	Last date of known prescription coverage (date of last prescription fill plus days' supply minus one day) and a grace period equal to 30 days*
End of study data	Date of death#, Date of end of registration, Date of Study End

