#### 9.7.4 Meta-analysis

After evaluating potential treatment effect heterogeneity we may pool results from the two databases. Descriptive tables and all parameter estimates from the main and all sensitivity analyses will be pooled using meta-analytic methods assuming a fixed effects model, since random effects pooling can be biased in the context of few databases [R17-1410]. Calculation of an overall mean/proportion/hazard ratio from two databases reporting a single mean/proportion/hazard ratio will use the inverse variance method for pooling [R02-0971].

To correct variance for potential duplicates in pooling two databases for the primary outcome, the following method will be used. The variance correction for overlapping samples when pooling multiple databases was described by [REDACTED] and [REDACTED] [M20-0016].

[figure not shown]
The formula for the variance is given by

$$\hat{\sigma}_{combined}^2 = w_1^2 \hat{\sigma}_1^2 + w_2^2 \hat{\sigma}_2^2 + 2w_1 w_2 \rho \hat{\sigma}^2$$

Where

- $w_1$  and  $w_2$  are the weights applied to the two databases and  $w_2 = 1 - w_1$
- $\hat{\sigma}_1^2$  and  $\hat{\sigma}_2^2$  are the variance estimates from both databases
- $\rho$  is the % of overlapping observations in the smaller dataset
- $\hat{\sigma}^2 = (n_1 \hat{\sigma}_1^2 + n_2 \hat{\sigma}_2^2) / 2$  where  $n_1$  and  $n_2$  are the number of observations in both databases

Given that an exact overlap is not known between databases, estimates in 10% intervals will be used to assess varying degrees of variance in the pooled point estimates. The pooled analyses will be conducted using R package **rmeta** in R studio [R20-1986, M20-0016].

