## **9.9 LIMITATIONS OF THE RESEARCH METHODS**

There are several methodological challenges when conducting epidemiologic studies to evaluate the association between glucose lowering drugs and outcomes of interest among patients with diabetes. These challenges include, but are not limited to, changes in treatment in response to advancing diabetes or due to adverse effects of specific drugs and time-varying

risk of an outcome [[P12-13528](#), [P14-17457](#), [R14-4378](#)]. Other limitations of the study are listed below.

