10.3 MAIN ANALYSIS

Please check study protocol section 9.7.3.

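### The log-rank test named as the proportional-hazards check tests whether the HR is 1, not whether it is constant over time

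*Protocol*

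**What the plan says.** Protocol 9.7.3 sets the main model: "Cox proportional hazards regression models based on time-to first acute pancreatitis event will be used to estimate hazard ratios (HR) and 95% CIs". The section closes with the only diagnostic for that model in the published text: "Proportionality hazard assumption will be checked using the log rank test". For the main analysis, SAP 10.3 says "Please check study protocol section 9.7.3" and adds nothing. The sensitivity analyses in Protocol 9.7.6 include no proportional-hazards check and no HR by follow-up period. Neither document says what follows if the check passes or fails.

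Three other places bear on the point:
- Protocol 9.5 frames the comparison as "non-inferiority" against a ratio of 1.5 and states: "It is assumed that all patients have 1 year of follow up".
- Protocol 9.7.1 defines follow-up so that it "Starts from the day after the index date until the first qualifying event has been met". Its length therefore varies between patients.
- Protocol 9.9 lists among the challenges "changes in treatment in response to advancing diabetes or due to adverse effects of specific drugs and time-varying" risk of an outcome.

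Protocol 9.7.5 and SAP 10.5 are absent from the published text and are not held against the plan.

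**The concern.** The log-rank test has equal hazards in the two groups as its null hypothesis. The proportional-hazards assumption is a different statement: the ratio of the hazards, whatever its value, does not change over follow-up. A test of the first cannot serve as a check of the second, and it misleads in both directions:
- A constant harmful or protective effect gives a significant log-rank result, which under the plan would read as a violated assumption.
- An early excess followed by a later deficit can average out near 1. The result is then non-significant and would read as support for the assumption.

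The main result is one pooled HR in a safety study. If the HR changes over time, that figure is an average whose value depends on when events fall, and as-treated censoring shapes that timing. The named check cannot reveal this. Time-varying outcome risk, which the protocol acknowledges, is not the same as a changing HR, but it is a setting where a valid check is useful.

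**Working it through.** **Inputs (Protocol 9.5).** Rate 0.0022 per person-year in both groups, ratio 1.5, one-sided alpha 0.05, power 80%, 1:1 allocation, 1 year of follow-up, 34585.4 per group.

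**Planned size reproduced.** Farrington-Manning with restricted ML variance: n = [(1.645·s0 + 0.842·s1)/(1.5·0.0022 − 0.0022)]². The restricted control rate is about 0.00176, so s0 ≈ 0.0812 and s1 ≈ 0.0845. This gives n = 34585.41 against the stated 34585.4. Comparator events are 34585.4 × 0.0022 = 76.1, or about 38 per half-year.

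**Illustration.** The documents give no hazard pattern, so the HR patterns are assumptions, each with any change at 6 months and tests at two-sided 5%. Events are rare, groups are equally at risk, counts are Poisson and times are uniform within each half-year.

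- Log-rank: z = (exposed events − d/2)/√(d/4), with d the total events.
- Treatment-by-time score test: z = Σ(g − ḡ)(x − p)/√[p(1 − p)Σ(g − ḡ)²]. Here x = 1 for an exposed event, p is the exposed share of events, and g = t or log t.

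Expected log-rank z by hand:
- Constant 1.5: exposed 114.1, d = 190.2, z = 19.02/6.90 = 2.76, rejection about 79%.
- 1.6 then 0.6: exposed 83.7, d = 159.8, z = 3.80/6.32 = 0.60, rejection about 9%.
- 1.6 then 1.0: exposed 98.9, d = 175.0, z = 11.41/6.61 = 1.73, rejection about 41%.

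Simulated rejection rates (%, 40,000 runs each) for all events / a database with 50% of them / one with 30% (the shares are assumptions):

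| HR pattern | Log-rank | Linear time | Log time |
|---|---|---|---|
| Constant 1.5 | 79 / 49 / 33 | 5 / 5 / 5 | 5 / 5 / 5 |
| 1.6 then 0.6 | 9 / 7 / 6 | 72 / 44 / 29 | 49 / 29 / 19 |
| 1.6 then 1.0 | 41 / 24 / 16 | 26 / 15 / 11 | 18 / 11 / 9 |

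At a constant HR of 1.0 every test rejects about 5%. In the third row log-rank responds to the average HR, (1.6 + 1.0)/2 = 1.30, and not to the fade.

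**Second simulation.** This one tracked risk sets explicitly at 34,585 per group (4,000 runs), comparing log-rank with a linear treatment-by-time test. A constant HR of 1.5 gave 80.5% v 5.1%. An HR of 1.5 then 0.5 gave 5.1% v 78.6%.

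**Uneven follow-up.** Let comparator event times have density proportional to exp(−kt) over 0 to 5 years, with the same 76.1 events. For k = 1 and k = 2, 40% and 63% of them fall in the first half-year.

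| HR pattern | Log-rank (k = 1, 2) | Linear | Log |
|---|---|---|---|
| Constant 1.5 | 80, 79 | 5 | 5 |
| 1.6 then 0.6 | 5, 27 | 55, 58 | 63, 44 |
| 1.6 then 1.0 | 28, 58 | 18, 21 | 22, 17 |

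The average HR in the reversal moves with follow-up alone. It is 0.5 × 1.6 + 0.5 × 0.6 = 1.10 in the 1-year case, 0.40 × 1.6 + 0.60 × 0.6 = 1.00 for k = 1, and 0.63 × 1.6 + 0.37 × 0.6 = 1.23 for k = 2.

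**Precision of period HRs.** At HR 1 the 95% CI is exp(±1.96·√(2/n)), with n events per group in the period. For n = 38 it is 0.64 to 1.57, and for n = 19 it is 0.53 to 1.89. For n = 11.4 (a half-year in a database with 30% of events) it is 0.44 to 2.27.

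**The case against.** The strongest reply is that little depends on this check. It changes no estimate, interval, margin or pooling step, and the plan attaches no decision to it, so the worst outcome is a mislabelled diagnostic p-value. That is right as far as it goes, and it is why the point does not invalidate the analysis. The p-value would still be used to support or question the reading of the main result.

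A valid test is also weak at this event count. In a database with 30% of events it finds a reversal from 1.6 to 0.6 in about 29% of studies, and a fade to 1.0 in about 11%. Neither time function is better in every pattern, and period HRs are imprecise. All of this stands. It argues for a plot and a plain statement of limited power, not for keeping a test of a different hypothesis.

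The hazard patterns are assumed, and nothing in the documents indicates non-proportional hazards here. That stands too: the figures illustrate how the test behaves and predict nothing about the data.

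The 12-month intention-to-treat analysis in Protocol 9.7.6 gives an HR over a common horizon, which partly answers the dependence on when as-treated follow-up ends. It does not test whether the HR is constant. The authors may have meant log(−log) survival plots, but the text does not say so.

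**Conclusion.** The concern holds. The sentence in Protocol 9.7.3 names a test of the wrong hypothesis, and nothing in the published text corrects it. This follows from what the log-rank test is and needs no simulation.

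The size is illustrative and rests on the planned event count, the 1-year assumption and the assumed HR patterns. With all events, the named check rejects about 79% of the time when a constant HR of 1.5 satisfies the assumption. It rejects about 9% of the time when the HR goes from 1.6 to 0.6 and the assumption fails. The correction should be made before analysis. It affects interpretation of the HR only.

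**What to change.** **Core correction, one sentence.** In Protocol 9.7.3, replace the log-rank check with a scaled Schoenfeld residual test or a treatment-by-time term in the PS-matched Cox model, run in each database.

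**To complete it, a few SAP sentences:**
- Fix the time function before analysis and add a residual or log(−log) plot.
- State that a non-significant result does not confirm proportionality.
- Fix one set of follow-up periods and report HRs for them beside the overall HR, as descriptive results, whatever the test shows.
- If the check is to be combined across databases, use the treatment-by-time term, which gives a coefficient and standard error. Protocol 9.7.4 already says that combined estimates "will use the inverse variance method for pooling".

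**Cost.** One test, one plot and one small table per database. The period HRs will be imprecise and should be labelled so. Sample size, margin and alpha do not change.
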